F 2.1 Patients with baseline eGFR \geq 40 mL/min/1.73 m²

F 2.1.1 Serum creatinine increase to \geq 1.5-fold from baseline

- Assess the patient to identify and manage any potential contributing factor. Correct any dehydration and ensure the patient is well hydrated prior to next renal safety monitoring visit.
- At the investigator's discretion, the patient may continue with study treatment, and retest of serum creatinine should be performed the following week. If the underlying cause (eg, dehydration) is still present at the next evaluation, the investigator should carefully consider if the retesting should be postponed for another week.
- Patient should attend the following week for repeat serum creatinine measurement. If an underlying potentially treatable cause (eg, dehydration) is still present, the investigator should treat this appropriately and postpone testing for up to a week.
- Subsequent management will depend on the repeat measurement(s):
 - If serum creatinine <1.5-fold of baseline value for two successive measurements, the patient may restart/continue with study treatment and the original study visit schedule.
 - If repeat serum creatinine is between ≥1.5 to <2.0-fold of baseline value, the patient should be evaluated every 1 to 2 weeks. During this evaluation period, the randomised treatment can be temporarily interrupted at the investigator's discretion. If serum creatinine is <1.5-fold of baseline value during the evaluation period, study treatment may be restarted/continued on the original study visit schedule.
 - If serum creatinine ≥2.0-fold of baseline value for 2 successive measurements (including the original high value if applicable), randomised treatment should be permanently discontinued and the patient should be followed up as per study schedule.

F 2.2 Patients with baseline eGFR <40 mL/min/1.73 m²

The CKD-EPI formula (Michels et al 2010) should be used to estimate GFR for enrolment criteria, baseline value and subsequent on-study measurements.

More intense renal monitoring and discontinuation are based on % drop from the baseline value.

F 2.2.1 If eGFR drops to <75% of the baseline value

- Assess the patient to identify and manage any potential contributing factor. Correct any dehydration and ensure the patient is well hydrated prior any future evaluation.

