- At the investigator's discretion, the patient may continue with study treatment and retest of serum creatinine should be performed within 7 days. If the underlying cause (eg, dehydration) is still present at the next evaluation, the investigator should carefully consider if the retesting should be postponed for another week.
- Subsequent management will depend on the repeat measurement(s):
 - If eGFR is >75% of the baseline value on 2 successive measurements, the patient may restart/ continue with study treatment on the original study visit schedule.
 - If the repeat eGFR value is between 60% and 75% of the baseline value, the patient should be evaluated every 1 to 2 weeks for serum creatinine measurements/ GFR estimation. During this evaluation period, the randomised treatment can be temporarily interrupted at the investigator's discretion. If eGFR returns to >75% of baseline value during the evaluation period, study treatment may be restarted/ continued on the original study visit schedule.
 - If eGFR is <60% of the baseline value on 2 successive measurements, randomised treatment should be permanently discontinued, and the patient should be followed up as per study schedule.

Examples of eGFR changes and triggered actions

Baseline eGFR (mL/min/1.73 m ²)	Intense renal monitoring ± temporary interruption of treatment eGFR (mL/min/1.73 m ²)	Permanently discontinue randomised treatment eGFR (mL/min/1.73 m ²)
39	23 to 29	<23
36	21 to 27	<21
32	19 to 24	<19
28	17 to 21	<17
25	15 to 19	<15

REFERENCE

Michels et al 2010

Michels WM1, Grootendorst DC, Verduijn M, Elliott EG, Dekker FW, Krediet RT. Performance of the Cockcroft-Gault, MDRD, and new CKD-EPI formulas in relation to GFR, age, and body size. Clin J Am Soc Nephrol. 2010 Jun;5(6):1003-9.

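### The eGFR example table in Appendix F 2.2.1 does not match the 60% and 75% rules it illustrates; read in whole numbers, one boundary value in each of four rows gets a different action

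*Supplement*

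**What the plan says.** Appendix F 2.2 of the protocol (version 5.0) covers patients with baseline eGFR below 40 mL/min/1.73 m². It states the principle first: "More intense renal monitoring and discontinuation are based on % drop from the baseline value".

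Section F 2.2.1 then gives the rules:

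- The section is entered under the heading "If eGFR drops to <75% of the baseline value".
- Restart or continuation: "If eGFR is >75% of the baseline value on 2 successive measurements".
- Closer evaluation every 1 to 2 weeks, with interruption at the investigator's discretion: "If the repeat eGFR value is between 60% and 75% of the baseline value".
- Stopping: "If eGFR is <60% of the baseline value on 2 successive measurements, randomised treatment should be permanently discontinued".

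A table titled "Examples of eGFR changes and triggered actions" follows. For five baselines it gives a monitoring range and a limit for permanent discontinuation, all in whole numbers: 39 (23 to 29; below 23), 36 (21 to 27; below 21), 32 (19 to 24; below 19), 28 (17 to 21; below 17) and 25 (15 to 19; below 15). It states no rounding rule, and its stopping column does not mention two consecutive readings.

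Sections 7.1 and 8.4.5 send investigators to Appendix F for renal events.

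**The concern.** A worked example should reproduce the rule above it. Here some values in the monitoring column are below 60% of baseline, where the text calls for stopping if the reading is repeated. One value is above 75%, where the text does not open the section at all. A site that reads the table and a site that computes the percentage could take different actions on the same result.

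The patients concerned have the lowest kidney function in the trial: eligibility starts at eGFR 25, so baselines of 25 to 39 are part of the intended population. Section 2.3 names creatinine elevation as the main toxicity of concern with verinurad monotherapy. At stake is uniform handling of study drug near the limits, and with it the consistency of recorded interruptions and discontinuations.

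**Working it through.** **Inputs.** Baselines and table limits come from the example table in Appendix F 2.2.1, and the 60% and 75% rules from the text above it. The precision of reported eGFR is not stated; whole numbers are assumed first, as in the table, and decimals are checked afterwards.

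**Step 1: exact limits.** Lower limit = 0.60 × baseline; upper limit = 0.75 × baseline.

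| Baseline | 60% | Table lower limit | 75% | Table upper limit |
|---|---|---|---|---|
| 39 | 23.4 | 23 | 29.25 | 29 |
| 36 | 21.6 | 21 | 27.0 | 27 |
| 32 | 19.2 | 19 | 24.0 | 24 |
| 28 | 16.8 | 17 | 21.0 | 21 |
| 25 | 15.0 | 15 | 18.75 | 19 |

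**Step 2: can a rounding rule reproduce the table?**

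- Nearest integer gives 9 of 10 limits. It fails at baseline 36, where 21.6 rounds to 22 and the table has 21.
- Rounding down fails at baseline 28 (16 against 17) and at the upper limit for 25 (18 against 19).
- Rounding up fails at baseline 39 (24 against 23, and 30 against 29), at 36 (22 against 21) and at 32 (20 against 19).

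None of the three gives the whole table.

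**Step 3: whole-number values that get different actions.** Ratio = eGFR ÷ baseline.

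| Baseline | eGFR | Ratio | Text | Table |
|---|---|---|---|---|
| 39 | 23 | 23/39 = 59.0% | stop, if repeated | monitor |
| 36 | 21 | 21/36 = 58.3% | stop, if repeated | monitor |
| 32 | 19 | 19/32 = 59.4% | stop, if repeated | monitor |
| 28 | none | 17/28 = 60.7% at the lower limit | – | – |
| 25 | 19 | 19/25 = 76.0% | above 75% | monitor |

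So one value conflicts in each of four rows: three at the stopping limit and one at the monitoring limit. The whole numbers from 60% to 75% are 24–29, 22–27, 20–24, 17–21 and 15–18 for the five baselines in order.

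This count places exactly 75% (27/36, 24/32, 21/28) inside the monitoring band. The text leaves that case open: the section heading requires less than 75%, continuing requires more than 75%, and the band runs between 60% and 75%.

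**Step 4: decimals.** If the table limits are read as exact cut-points, all five rows differ somewhere:

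- 39: 23.0 up to 23.4 (width 0.4), and 29.0 to 29.25 (0.25).
- 36: 21.0 up to 21.6 (0.6, the widest).
- 32: 19.0 up to 19.2 (0.2).
- 28: 16.8 up to 17.0 (0.2). Here the table stops where the text monitors, the reverse of the first three rows.
- 25: 18.75 to 19.0 (0.25).

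**The case against.** The strongest reply is that the table is rounded illustration. The text says the actions rest on percentages, the table is headed as examples, and for any baseline not listed a site has to compute the percentage anyway. Nearest-integer rounding accounts for nine limits, so only one cell is really mis-rounded. If values are themselves reported as whole numbers, a 23 on a baseline of 39 could lie anywhere from 22.5/39.5 = 57% to 23.5/38.5 = 61%, which straddles the limit. Stopping also needs two readings under 60%, so a single value in the gap does not trigger it.

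Much of this stands, and it limits the point to boundary values. It does not remove the conflict: two successive readings of 23 on 39 mean stopping by the text and monitoring by the table, however the limit came to be rounded. Nor does the protocol say which governs when the two disagree.

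The baseline 25 row is the weakest as a safety matter. The table there leans toward more observation, and for a patient already under evaluation one rule asks for two readings above 75% before continuing, so a single 19 is not clearly a case for continuing.

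A reader might infer that the table contradicts the stopping rule throughout four rows, that patients are exposed to a serious renal risk, or that discontinuation counts will be distorted. The documents do not support these readings. Each whole-number conflict is a single value. Section 2.3 ties the creatinine concern to monotherapy, reports no elevations in the three studies combining verinurad with a xanthine oxidase inhibitor, and reports equal rates in the active and placebo groups of the Phase 2a study. Nothing in the protocol shows how often patients would fall in the gaps.

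**Conclusion.** The mismatch is real and small. One limit (21 against 21.6 for baseline 36) fits no nearest-integer rule. Under whole-number reading, text and table lead to different actions at one boundary value in each of four rows. That count rests on two assumptions: whole-number eGFR, and exactly 75% counted within the monitoring band. With decimals every row has a gap, the widest 0.6 mL/min/1.73 m². Separately, the table drops the condition of two consecutive readings for stopping, which holds whatever the precision.

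The effect on discontinuation counts cannot be quantified from the documents. The sample size calculation and the alpha do not depend on these limits, and Section 9.4.2.1 keeps post-discontinuation data in the primary analysis, so a marginal difference in stopping does not remove patients from it. The correction is still worth making, because these limits decide whether study drug is stopped. Which limit is clinically right is not for this review to say.

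**What to change.** Reconcile the text and the table of Appendix F 2.2.1:

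1. Have the clinical team confirm the limits, including the handling of a value at exactly 75%.
2. Recompute all ten table limits from them, with one stated rounding rule and the stated precision of eGFR.
3. Carry the confirmed repeat-measurement condition into the stopping column, or refer there to the text.
4. State whether the percentage or the table governs at a boundary value.
5. Inform sites.

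The cost is one corrected table, a sentence or two of text and a clarification letter. No data collection or analysis changes.
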